$$H_0: [\pi_1/(1 - \pi_1)]/[\pi_0/(1 - \pi_0)] \leq 1 \text{ versus } H_A: [\pi_1/(1 - \pi_1)]/[\pi_0/(1 - \pi_0)] > 1$$

Primary efficacy variable 2 will be analyzed at each post-baseline visit using a logistic regression model with treatment and baseline LDL-C as explanatory variables (Stokes et al. 2012). The odds ratio, two-sided 97.5% confidence interval for the odds ratio, and p-value based on the fitted model will be reported. If the p-value based on a two-sided test for inclisiran + usual care versus usual care at Day 330 is < 0.025 and the corresponding odds ratio is greater than 1, statistical significance in favor of inclisiran + usual care is shown. In case of non-

convergence of a logistic regression model, the model will be updated to use Firth's penalized likelihood method (Firth 1993). If the model using Firth's method still shows convergence issues then the baseline LDL-C covariate may be removed from the model. Two-sided 97.5% confidence intervals for the proportion of participants who achieve LDL-C < 70 mg/dL in each treatment group will be calculated, using the normal approximation to the binomial distribution.

The primary analysis of primary efficacy variable 2 will be based on the FAS. The primary analysis of this variable will be repeated for the Per-Protocol Set, Restricted Set 1, and Restricted Set 2.

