- Summary measure: Treatment difference ($[\text{inclisiran + usual care}] - \text{usual care}$) in the proportion of participants who achieve LDL-C < 70 mg/dL

For the above estimand, primary efficacy variable 2 will be analyzed at each post-baseline visit for the FAS using the two-sample z-test (normal approximation to the binomial distribution) to compare inclisiran + usual care versus usual care. Two-sided 97.5% confidence intervals will be calculated, using the normal approximation to the binomial distribution.

For both primary efficacy variables 1 and 2, additional sensitivity analyses will be conducted by repeating the corresponding primary analyses on participants in the Full Analysis Set but excluding participants with baseline LDL-C < 70 mg/dL.

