2.6.2 Statistical hypothesis, model, and method of analysis

Analyses of secondary efficacy variables 1 and 7 - 20 will be similar to the primary analysis of primary efficacy variable 1 (using MMRM, but with a two-sided 95% confidence interval for the treatment difference).

Secondary efficacy variables 2, 3, and 22 will be analyzed using an analysis of covariance (ANCOVA) linear model with treatment and baseline LDL-C as explanatory variables. Least-squares mean of each treatment group, 95% confidence interval for the treatment group least-squares means, least-squares mean treatment difference, 95% confidence interval for the treatment difference, and p-value based on the fitted model will be reported. Variables 2 and 3 are calculated by averaging the observed post-baseline values (change or percent change) for each participant across analysis visits Day 90, Day 270, and Day 330. The outcome value for variable 22 is a proportion that is calculated for each participant with total number of study days equal to duration on study as defined in Section 2.3.1.

Secondary efficacy variables 4 - 6 and 23 will be analyzed at each applicable post-baseline visit using a logistic regression model with treatment and baseline LDL-C as explanatory variables (Stokes et al. 2012). The odds ratio, 95% confidence interval for the odds ratio, and p-value based on the fitted model will be reported. Confidence intervals for the percentages per treatment group will be presented and will be derived from the normal approximation to the

binomial distribution. Missing data will be imputed using “non-responder” (i.e., “negative” outcome) imputation.

Secondary efficacy variable 21 will be analyzed at each post-baseline visit using a proportional odds model with treatment and baseline LDL-C as explanatory variables (Stokes et al. 2012). The odds ratios, 95% confidence intervals for the odds ratios, and p-values based on the fitted model will be reported. Confidence intervals for the percentages per treatment group will be presented and will be derived from the normal approximation to the binomial distribution. Missing data will not be imputed.

Analyses of secondary efficacy variables will be based on the FAS.

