2.13 Interim analysis

After all participants complete their baseline visit, the demographic and baseline characteristics may be summarized to help design new studies. No analysis will be performed using post-baseline data. Thus, there is no need to adjust the level of significance for such interim analysis of baseline data.

3 Sample size calculation

The sample size was calculated for the two primary efficacy variables with adjustment for multiple testing by using the Bonferroni procedure.

For primary efficacy variable 1, i.e., percent change from baseline in LDL-C, the standard deviation is assumed to be 40, partly based on the results from ORION-10 and ORION-11 clinical trials and considering that the standard deviation will likely be larger in this trial since changes in lipid-lowering therapy are allowed in both treatment groups. An expected mean treatment difference of 15 is assumed, which is smaller than the mean difference observed in the Phase III trials, to account for 1) potential lower utilization of background lipid-lowering therapy in the inclisiran + usual care treatment group compared to the usual care treatment group, and 2) the ability to add non-statin lipid lowering therapy in the usual care treatment group. A z-test, an allocation ratio of 1:1, and a two-sided significance level of 0.025 were also used in the calculation of sample size.

[Table 3-1](#) considers total sample sizes for expected mean treatment differences of 10, 15, and 20, and powers of 0.85 and 0.90 (nQuery Version 8.4.1.0). From [Table 3-1](#), an expected mean treatment difference of 15 (based on means of 40 and 55 at Day 330 in the usual care and inclisiran + usual care treatment groups, respectively) and a power of 0.85 were chosen to provide a total sample size of 306 participants.

Table 3-1 Sample Size Calculations for Percent Change from Baseline in LDL-C

Mean treatment difference	Power = 0.85	Power = 0.90
10	688	796
15	306	354
20	172	200

For primary efficacy variable 2, i.e., achieving LDL-C < 70 mg/dL (yes, no), a z-test, an allocation ratio of 1:1, and a two-sided significance level of 0.025 were used in the calculation of sample size.

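### Per-arm percentages get normal-approximation intervals with no small-count fallback, so coverage falls short in small subgroup categories and in any statin-intensity category that proves rare

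*SAP*

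**What the plan says.** **Primary variable 2 (SAP 2.5.2).** "Two-sided 97.5% confidence intervals for the proportion of participants who achieve LDL-C < 70 mg/dL in each treatment group will be calculated", and the method is the normal approximation. If the logistic model does not converge, the SAP moves to Firth's penalised likelihood. The percentage interval has no corresponding fallback.

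**Subgroups (SAP 2.2.1 and 2.5.7).** The 2.5.2 approach is applied separately within each subgroup category. A category is shown once it holds 10 participants across both arms. The list includes five eGFR bands, statin intolerance and LDL-C quartiles. SAP 1.1 says randomisation is not stratified.

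**Secondary variables 4–6, 23 and 21 (SAP 2.6.2).** "Confidence intervals for the percentages per treatment group will be presented and will be derived from the normal approximation to the binomial distribution". The level of these intervals is not stated. For the odds ratios beside them it is: "The odds ratio, 95% confidence interval for the odds ratio, and p-value based on the fitted model will be reported". I take the percentage intervals to be 95% as well. Variable 21 sorts participants into decrease, no change or increase in statin intensity at each visit, and missing values are not imputed.

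**Risk difference (SAP 2.5.5).** "Two-sided 97.5% confidence intervals will be calculated, using the normal approximation to the binomial distribution". Protocol 12.4.5 also specifies this. The per-arm percentage intervals appear only in the SAP.

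**The concern.** The Wald interval estimates its own standard error from the observed proportion. When the count is small, or the proportion is near 0 or 1, that standard error is too small, and at 0% or 100% it is zero. The interval then covers less often than its label says, can extend outside 0–100%, or collapses to a point.

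The plan opens the door to such cells through the low display threshold for subgroups and through a three-category outcome whose expected rates are not given. The Firth fallback shows that sparse cells were foreseen for the odds ratio. A cell with 0% or 100% responders is a standard cause of non-convergence, and it is also the cell in which the Wald interval degenerates. At stake is whether the error bars printed beside subgroup and statin-intensity percentages mean what they say.

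**Working it through.** **1. The plan's own figures (SAP Section 3).** Inputs: "the standard deviation is assumed to be 40"; "An expected mean treatment difference of 15 is assumed"; rates 0.55 and 0.75; two-sided alpha 0.025 (z = 2.2414); power 0.85 (z = 1.0364); 1:1 allocation; 20% loss.

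- Variable 1: n per arm = 2 × 40² × (2.2414 + 1.0364)² / 15² = 152.8, so 153 per arm and 306 in total. This matches.
- Variable 2, pooled variance with mean rate 0.65: n per arm = [2.2414√(2 × 0.65 × 0.35) + 1.0364√(0.55 × 0.45 + 0.75 × 0.25)]² / 0.20² = 120.5, so 121 per arm and 242 in total. This matches.
- 306 / 0.80 = 382.5, so 384 with equal arms (192 each). This matches.

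The SAP states no coverage figure, so the rest is new calculation.

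**2. Method.** For x events in n with p̂ = x/n:

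- Wald: p̂ ± z√(p̂(1 − p̂)/n)
- Wilson: [p̂ + z²/(2n) ± z√(p̂(1 − p̂)/n + z²/(4n²))] / (1 + z²/n)
- Exact coverage at true rate p: the sum of binomial probabilities over every x whose interval contains p.

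**3. Smallest displayable subgroup.** Ten participants split evenly give n = 5 per arm. With z = 2.2414 and p = 0.75:

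| x of 5 | Probability | Wald 97.5% | Contains 0.75? |
|---|---|---|---|
| 0 | 0.0010 | 0% to 0% | no |
| 1 | 0.0146 | −20.1% to 60.1% | no |
| 2 | 0.0879 | −9.1% to 89.1% | yes |
| 3 | 0.2637 | 10.9% to 109.1% | yes |
| 4 | 0.3955 | 39.9% to 120.1% | yes |
| 5 | 0.2373 | 100% to 100% | no |

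Wald coverage = 0.0879 + 0.2637 + 0.3955 = 74.7%. Wilson misses only x = 0 and x = 1, so it covers 98.4%. The chance of a zero-width Wald interval is 0.75⁵ + 0.25⁵ = 23.8%.

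With n = 10 per arm and p = 0.75, Wald covers for x = 5 to 9: 0.0584 + 0.1460 + 0.2503 + 0.2816 + 0.1877 = 92.4%. Wilson covers 98.0%. At the planned usual-care rate of 0.55 and n = 5, Wald covers 93.1%.

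**4. Variable 21, nominal 95%.** The category rates are assumptions. Sizes are 192 (all randomised in one arm) and 153 (306/2, because missing values are not imputed).

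| Assumed rate | n = 192 Wald | n = 192 Wilson | n = 153 Wald | n = 153 Wilson |
|---|---|---|---|---|
| 1% | 85.4% | 95.5% | 78.4% | 93.2% |
| 2% | 89.3% | 93.9% | 80.9% | 96.5% |
| 5% | 91.3% | 95.5% | 94.0% | 94.0% |
| 10% | 93.7% | 94.7% | 93.9% | 94.3% |

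With 1, 2 or 3 events in 192, the Wald lower limits are −0.50%, −0.39% and −0.19%; Wilson gives +0.09%, +0.29% and +0.53%. With no events, Wald gives 0 to 0 and Wilson 0 to 2.0%. The chance of 1–3 events in 192 is 73% at a 1% rate, 44% at 2% and 1% at 5%.

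**5. Full-sample primary intervals, nominal 97.5%, n = 192.** Per-arm percentages: 97.1% at 0.55 and 97.5% at 0.75. Risk difference, by joint enumeration of both arms: 97.4% at 0.75 vs 0.55, 97.5% at 5% vs 5%, and 97.7% at 2% vs 2%.

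**The case against.** Several broader readings are tempting, and the documents do not support them.

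- **That the risk-difference interval is also deficient.** It holds its level at the planned rates and at rare ones (step 5), and a negative limit is legitimate for a difference. SAP 2.5.7 does not carry it into subgroups.
- **That variable 4 (LDL-C < 100 mg/dL) will sit near 95% success.** At Day 330, missing values count as failures, and with the planned 20% loss success cannot exceed about 80%.
- **That variable 23 (statin discontinuation) is rare.** SAP 2.6.1 codes all early terminators as discontinued, so 20% loss puts the rate near 20% or higher, where Wald covers 95.0% at n = 192.
- **That rare safety outcomes are affected.** MACE components get counts, percentages and hazard ratios, and adverse events get risk ratios. Neither gets a percentage interval of this kind.
- **That variable 21 is known to have rare categories.** The SAP gives no rates. A decrease includes stopping the statin. Protocol 4.1 cites about one-third discontinuing over three years, crudely 11% per year; at 10% and n = 192, Wald loses only about one point to Wilson.

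It is also fair to say that these are descriptive per-arm intervals, since between-arm evidence rests on the odds ratios. And 74.7% belongs to one combination of rate and size. If 0.75 is the rate among participants with data, counting 20% missing as failures gives 0.80 × 0.75 = 0.60. At n = 5 Wald then misses only x = 0 and x = 5, and covers 1 − 0.40⁵ − 0.60⁵ = 91.2%.

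All of this stands and limits the point. It does not remove the small-subgroup problem, which needs no rare-event assumption, or the lack of protection if a variable 21 category proves rare.

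**Conclusion.** The point holds in a narrow form, at low severity. In subgroup categories near the display threshold, the nominal 97.5% Wald interval for a per-arm percentage can fall well short: 74.7% at n = 5 and 92.4% at n = 10 for a rate of 0.75. It can also leave the 0–100% range or shrink to zero width. For variable 21, coverage falls to 78–89% if a category has a rate of 1–2%, and the gap largely closes by 10%.

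This rests on four assumptions:

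- SAP 2.5.7 brings the percentage intervals of 2.5.2 into the subgroups along with the logistic model.
- Small categories split about evenly between arms. Randomisation is unstratified, so some arms could be smaller still.
- The 2.6.2 percentage intervals are 95%.
- The variable 21 rates are illustrative only.

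Full-sample primary percentages are already adequate. A reader might infer that the primary conclusion or the trial's size is in doubt; neither depends on these intervals.

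**What to change.** In SAP 2.5.2 and 2.6.2, name the Wilson score interval for per-arm percentages in place of the normal approximation, and state its level in 2.6.2. SAP 2.5.7 then inherits the change.

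Leave unchanged the risk-difference interval and z-test in 2.5.5 and the logistic and proportional-odds models. Changing the 2.5.5 interval would depart from Protocol 12.4.5 for almost no gain: the Newcombe interval covers 97.5% at 0.75 vs 0.55, against 97.4% now.

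The cost is two wording edits and one procedure option in the programs. No protocol amendment is needed for this, because the protocol does not specify per-arm percentage intervals. At the full-sample primary rates coverage barely moves.

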Secondary efficacy variables 4 - 6 and 23 will be analyzed at each post-baseline visit using a logistic regression model with treatment and baseline LDL-C as explanatory variables (Stokes et al 2012). The odds ratio, 95% confidence interval for the odds ratio, and p-value based on the fitted model will be reported. Missing data will be imputed using "non-responder" (i.e., "negative" outcome) imputation.

Secondary efficacy variable 21 will be analyzed at each post-baseline visit using a proportional odds model with treatment and baseline LDL-C as explanatory variables (Stokes et al 2012). The odds ratios, 95% confidence intervals for the odds ratios, and p-values based on the fitted model will be reported. Missing data will not be imputed.

Analyses of secondary efficacy variables will be based on the Full Analysis Set.

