1.1 Study design

[figure not shown]
This is a randomized, parallel-group, open-label, multicenter study comparing an LDL-C management strategy including inclisiran plus usual care with usual care. A total of approximately 384 participants will be randomized 1:1 to aggressive LDL-C management with inclisiran plus usual care (intervention arm) and usual care (control arm). Identification of participants will take place during hospitalization or in the weeks following discharge with screening soon thereafter. Screening of participants must take place within 5 weeks after discharge. The randomization schedule will not be stratified by any factors.

Potential participants who are discharged after an ACS on statin therapy (which is considered routine care) or have documented statin intolerance will be screened and receive an LDL-C test within 5 weeks post-discharge (to allow for the realization of the full effect of statin therapy). After the LDL-C test, participants with an LDL-C ≥ 70 mg/dL are eligible for the trial as long as they meet all other inclusion criteria. Participants will be randomized to inclisiran + usual care or usual care. All participants will be maintained on statin therapy during inclisiran treatment, but concomitant lipid-lowering therapy and LDL-C assessments will be at the discretion of the treating (primary) physician, mimicking real-world clinical decision-making and enabling the evaluation of inclisiran compared to usual care in patients with a recent ACS. Usual care may therefore include addition of ezetimibe, proprotein convertase subtilisin/kexin type 9 (PCSK9)-inhibiting monoclonal antibodies and/or commercially available inclisiran (Note: participants treated with inclisiran should not be treated with PCSK9-inhibiting monoclonal antibodies). After randomization, the treating physician will not have access to LDL-C values obtained as part of the study but will be able to perform LDL-C assessments at their discretion, to mimic usual care. The rationale of not providing the treating physician the LDL-C values obtained as part of the study is that those results might influence decisions made by him/her and could therefore undermine “usual care”. Commercially available inclisiran may be used for appropriate patients in the usual care arm at the sole discretion of the treating physician, without any influence from the PI. LDL-C measurement and assessment of lipid

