2.2.1 Subgroup of interest

Subgroup analyses of the two primary efficacy variables and the secondary endpoint of absolute change from baseline in LDL-C will be performed for the following subgroups (note that results for a subgroup category will only be presented if the total across both treatment groups within the category is at least 10 participants):

- Background lipid-lowering therapy at baseline: Yes, No
- Medical history of statin intolerance: Yes, No (from medical history statin intolerance CRF page)
- Baseline statin intensity: High, Moderate or Low, None
- Age: <65 years, >= 65 years
- Sex: Male, Female
- Race subgroup 1: White, Non-White/Multiple (unknown will be excluded from subgroup analyses)
- Race subgroup 2: White, Black or African American, Non-White/Non-Black or African American/Multiple (unknown will be excluded from subgroup analyses)
- Ethnicity: Hispanic or Latino, Not Hispanic or Latino (unknown or not reported will be excluded from subgroup analyses)
- BMI: >=30 vs < 30, and >=25 vs < 25 kg/m²
- Renal impairment by eGFR categories at baseline: <15, ≥15 to <30, ≥30 to <60, ≥60 to <90, or ≥90 mL/min/1.73m²
- Baseline LDL-C: <=100 and > 100 mg/dL; by median; and then by quartiles
- Index myocardial infarction: ST segment elevation myocardial infarction (STEMI), Non-ST-segment elevation myocardial infarction (NSTEMI), No myocardial infarction (from ACS medical history)
- Atrial fibrillation associated with index myocardial infarction: Yes, No (from ACS medical history)
- Revascularization procedure during index ACS event: Yes, No (from ACS medical history)
- History of diabetes: Yes, No (from ACS medical history)
- Baseline glycemic status: Diabetes, Pre-diabetes, Normoglycemia

For definition of baseline glycemic status, refer to Section [2.7.3, Table 2-4](#).

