intensity level to post-baseline lipid-lowering therapy addition group, and a shift table for statin intensity from baseline to Day 330/Last Visit will also be provided. To this end, the LLTs and statin intensity for Day 330/Last Visit will be assessed on the Day 330 visit date for participants with recorded Day 330 visit date, or on the study end date (date of last participation) otherwise. For the shift table for statin intensity from baseline to Day 330/Last Visit, the “None” category includes participants who did not take statin post baseline or who stopped the statin during the study.

Changes in LLTs prior to baseline will focus on statin and bempedoic acid taken within 30 days prior to study treatment start date, i.e. any time from day -30 to day -1. Number and percentage of participants will be presented for the following statin categories: initiation of statin therapy (no statin record present at day -30), discontinuation of statin therapy (no statin record present at day -1), increase in statin intensity, decrease in statin intensity, and change of statin within the same intensity group. Treatment gaps and/or overlapping treatment periods in case of two or more statins within the 30-day period will be ignored for analysis. If at least one statin record is present indicating that the statin was taken consistently on all days within the 30-day period, the participant will not be considered as having had any change in statin therapy.

For the analysis of lipid-lowering therapies at baseline a modified lipid-lowering therapy definition is also employed. For this analysis a modified lipid lowering therapy includes any statin, ezetimibe, PCSK9 inhibiting monoclonal antibodies, or bempedoic acid therapies.

The following medications will be included in the lipid-lowering therapy tables.

Table 2-3 Lipid-lowering Therapies

Medication	Medications included
Lipid Lowering Therapy	ATCCODE2=C10
Statin	ATCCODE2=C10 and CMDECOD contains ‘statin’, or ATCCODE4=C10AA, C10BA, or C10BX
Ezetimibe	ATCCODE2=C10 and CMDECOD contains ‘ezetimibe’
PCSK9 inhibiting monoclonal antibodies	ATCCODE2=C10 and CMDECOD contains ‘evolocumab’ or ‘alirocumab’
Bempedoic acid	ATCCODE2=C10 and CMDECOD contains ‘bempedoic acid’
Modified lipid lowering therapy	ATCCODE2=C10 and CMDECOD contains ‘statin’, ‘ezetimibe’, ‘evolocumab’, ‘alirocumab’, or ‘bempedoic acid’

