2.6.1 Secondary endpoint(s)

The secondary efficacy variables are the following:

1. Absolute change from baseline in LDL-C
2. Average percent change from baseline in LDL-C levels to each post-baseline visit
3. Average absolute change from baseline in LDL-C levels to each post-baseline visit

4. Achieving LDL-C < 100 mg/dL (yes, no) (among the subset of participants with LDL-C \geq 100 mg/dL at baseline)
5. Achieving \geq 50% reduction from baseline in LDL-C (yes, no)
6. Achieving LDL-C < 55 mg/dL (yes, no)
7. Percent change from baseline in apoB
8. Absolute change from baseline in apoB
9. Percent change from baseline in VLDL
10. Absolute change from baseline in VLDL
11. Percent change from baseline in non-HDL-C
12. Absolute change from baseline in non-HDL-C
13. Percent change from baseline in total cholesterol
14. Absolute change from baseline in total cholesterol
15. Percent change from baseline in Lp(a)
16. Absolute change from baseline in Lp(a)
17. Percent change from baseline in HDL-C
18. Absolute change from baseline in HDL-C
19. Percent change from baseline in triglycerides
20. Absolute change from baseline in triglycerides
21. Intensity of lipid-lowering therapy (decrease in dose, no change in dose, increase in dose)

Intensity of therapy is only available for statins, not for other lipid-lowering therapies used in this study. Therefore, for each participant and analysis visit, the highest statin intensity on each nominal visit date will be compared to baseline statin intensity. The decrease, no change, and increase in statin intensity at each visit will be assigned as follows:

Statin Intensity		Post-baseline Visit			
Baseline		High	Moderate	Low	None
	High	No change	Decrease	Decrease	Decrease
	Moderate	Increase	No change	Decrease	Decrease
	Low	Increase	Increase	No change	Decrease
	None	Increase	Increase	Increase	No change

22. Proportion of days covered (total number of days on either statin, ezetimibe, or PCSK9 inhibiting monoclonal antibody therapies divided by total number of study days)

If a participant did not take any of the three medications, then the total number of days will be assumed to be zero. Total number of study days is the total study duration (not treatment duration).

23. Discontinuation of statin therapy (i.e., no statin use \geq 30 days before the end-of-study visit) (yes, no)

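### The model for change in statin intensity (secondary variable 21) leaves out baseline statin intensity, which decides which changes are possible, and so gives up some power

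*SAP*

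**What the plan says.** Protocol 12.5.1 sets the model: "Secondary efficacy variable 21 will be analyzed at each post-baseline visit using a proportional odds model with treatment and baseline LDL-C as explanatory variables". SAP 2.6.2 repeats it, again "using a proportional odds model with treatment and baseline LDL-C as explanatory variables". SAP 2.6.1 narrows the variable to statins (recorded in SAP section 4, item 5), so that "the highest statin intensity on each nominal visit date will be compared to baseline statin intensity". A four-by-four table then sorts each pair of baseline and visit intensities into the three outcomes. In that table the High row contains no increase and the None row contains no decrease.

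Baseline intensity appears elsewhere in the SAP, but not in an inferential analysis of this variable:

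- SAP 2.2.1 lists it as a subgroup factor, "Baseline statin intensity: High, Moderate or Low, None". Those subgroup analyses cover only the two primary variables and absolute change in LDL-C.
- SAP 2.4.2 promises that "a shift table for statin intensity from baseline to Day 330/Last Visit will also be provided", which is descriptive.
- Sensitivity analyses of secondary variables are marked not applicable (SAP 2.6.4). The supplementary ones stop at variable 6 (SAP 2.6.5).
- SAP 1.1 states: "The randomization schedule will not be stratified by any factors".

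**The concern.** The outcome is defined relative to a baseline level, and that level rules out one of the three outcomes for two groups of participants. Both groups are to be expected here. Protocol 4.1 describes discharge on high-intensity statin as the guideline pathway, and inclusion criterion 7 admits statin-intolerant participants. Baseline LDL-C, the only covariate, plays no part in defining the outcome.

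Change in background therapy also matters to the design. The sample-size rationale lowers the expected LDL-C effect partly because the inclisiran arm may use less background therapy, and the open-label design is justified partly by the wish to study statin discontinuation. Variable 21 tests statin change directly, and no power is stated for it. Losing power by omitting a covariate that must be computed anyway is avoidable.

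**Working it through.** **1. Sample size.** The plan gives no figure for variable 21, only for the primary variables. For primary variable 1, n per arm = 2(z₀.₉₈₇₅ + z₀.₈₅)²σ²/δ² = 2 × (2.241 + 1.036)² × 40²/15² = 152.8, so 153 per arm and 306 in total, as stated. With 20% loss, 306/0.8 = 382.5, so 383; the plan rounds to 384, or 192 per arm. Missing values of variable 21 are not imputed, so evaluable n = 192 × 0.8 = 153.6, about 154 per arm (308 in total).

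**2. Assumed inputs (none are in the documents).** Baseline mix High/Moderate/Low/None: A = 80/12/3/5%, B = 65/20/5/10%, C = 45/30/10/15%. Usual-care percentages for decrease/no change/increase, by baseline level:

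| Setting | High | Moderate | Low | None |
|---|---|---|---|---|
| Little | 10/90/0 | 10/75/15 | 10/70/20 | 0/85/15 |
| Middle | 20/80/0 | 15/60/25 | 15/50/35 | 0/70/30 |
| Much | 35/65/0 | 20/40/40 | 15/35/50 | 0/50/50 |

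The conditional log odds ratio is -0.6 (odds ratio e^-0.6 = 0.55), towards lower intensity on inclisiran. For example, 20% decreasing from High becomes odds 0.25 × 1.822 = 0.456, or 31%. Mean baseline LDL-C shifts by 0.3 (in units of its within-level SD) per intensity level. Tests are two-sided at 0.05.

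One figure in the Protocol helps to place these rates. Section 4.1 cites about one third of patients stopping statins over three years. At a constant rate (an assumption) that is 1 - (2/3)^(1/3) = 12.6% in one year. This lies between the little and middle rates of decrease from High, before any dose reductions are counted.

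**3. Simulation.** 1,000 trials per row; planned model, then the same model plus baseline intensity as a four-level factor. Relative efficiency is the squared ratio of the mean z statistics.

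| Change, mix | Log OR (SE), planned | Log OR (SE), with factor | Power | Relative efficiency |
|---|---|---|---|---|
| Little, A | -0.607 (0.333) | -0.621 (0.336) | 0.450 → 0.457 | 1.03 |
| Little, B | -0.609 (0.322) | -0.626 (0.325) | 0.475 → 0.480 | 1.04 |
| Little, C | -0.580 (0.306) | -0.601 (0.309) | 0.479 → 0.496 | 1.05 |
| Middle, A | -0.579 (0.260) | -0.614 (0.263) | 0.618 → 0.654 | 1.10 |
| Middle, B | -0.569 (0.255) | -0.611 (0.259) | 0.622 → 0.668 | 1.11 |
| Middle, C | -0.566 (0.247) | -0.608 (0.252) | 0.627 → 0.674 | 1.12 |
| Much, A | -0.557 (0.228) | -0.623 (0.235) | 0.693 → 0.762 | 1.19 |
| Much, B | -0.537 (0.224) | -0.628 (0.232) | 0.669 → 0.780 | 1.28 |
| Much, C | -0.531 (0.220) | -0.621 (0.229) | 0.676 → 0.757 | 1.27 |

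In every row the standard error rises slightly (0.9% in the first, 0.336/0.333; 4.1% in the last, 0.229/0.220), and the estimate moves further from zero by more than enough to offset that. Under no effect (middle rates), rejection was 0.049 to 0.051 without the factor and 0.053 to 0.062 with it. The simulation error is √(0.05 × 0.95/1000) = 0.007, so 0.062 is 1.7 of these errors above 5%. A rank test stratified by baseline intensity gave nearly the same power as the model with the factor (0.663 against 0.668 in Middle, B).

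**4. Closed-form check (Middle, B).** Score decrease/no change/increase as -1/0/+1. Mean scores are High -0.20, Moderate 0.10, Low 0.20, None 0.30.

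- Overall mean: 0.65(-0.20) + 0.20(0.10) + 0.05(0.20) + 0.10(0.30) = -0.07.
- Total variance: 0.265 - 0.07² = 0.2601.
- Between-level variance: 0.65(0.13²) + 0.20(0.17²) + 0.05(0.27²) + 0.10(0.37²) = 0.0341, so R² = 0.131. Baseline LDL-C has R² = 0.009.
- Variance ratio, planned to adjusted: (1 - 0.009)/(1 - 0.131) = 1.14, in line with the simulated 1.11.

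Merging Moderate and Low (mean 0.12, deviation 0.19) gives 0.65(0.13²) + 0.25(0.19²) + 0.10(0.37²) = 0.0337 and R² = 0.130. In this case the three-level grouping loses almost nothing. Across all nine settings baseline intensity explained 5 to 25% of the score, against at most 2% for baseline LDL-C.

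**5. Chance imbalance.** With 65% on High and no stratification, the 95% range for the difference between arms in that share is ±1.96 × √(2 × 0.65 × 0.35/154) = ±11 percentage points.

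**The case against.** The strongest reply is that nothing here is an error. A reader might infer that the planned estimate is imprecise or biased towards no effect. The documents do not support that. Its standard error is the smaller of the two, and the gap between the two log odds ratios is non-collapsibility: they are different quantities. No secondary estimand is defined (SAP 1.2.2 is marked not applicable) that would make the conditional one the target. This stands in full.

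A reader might also infer that baseline intensity is the dominant predictor. Impossible cells do not show that, and 5 to 25% of the score variance under assumed rates is worthwhile, not dominant.

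The size of the gain is uncertain, and the documents partly point to the low end. Protocol 4.1.1 has participants entering without plans to adjust lipid-lowering therapy, and Protocol section 3 says statins are maintained during inclisiran treatment. If inclisiran shifts only decreases or only increases, the middle case gains only about 0 to 2 points.

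The added factor is not a complete cure. One proportional odds model with common cut-points still gives positive probability to impossible categories. A four-level factor can be unstable when Low and None are sparse: with few changes and mix A, up to 7 to 12% of simulated fits. The SAP's non-convergence rules cover the MMRM and binary logistic models only. These points shape the fix.

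The shift tables let a reader see who could move, but they carry no treatment comparison. Using baseline LDL-C as the covariate throughout is a tidy convention, but it fits this variable poorly.

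**Conclusion.** The point holds as a minor one about efficiency. The planned analysis of variable 21 is valid, with type I error near 5%, but it omits a baseline value that limits the possible outcomes and is needed to compute them. Under the assumptions listed, the omission costs roughly 1 to 11 points of power (relative efficiency 1.03 to 1.28). The low end applies if few participants change statin intensity and the high end if many do. The direction was the same in all nine settings. The size rests on assumed baseline mixes, change rates and a common conditional log odds ratio of -0.6. Variable 21 is one of 23 secondary variables and lies outside the Bonferroni split, so no primary conclusion changes.

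**What to change.** Before database lock, add baseline statin intensity as a factor to the proportional odds model for variable 21 in SAP 2.6.2. Use the grouping already in SAP 2.2.1 (High; Moderate or Low; None) to avoid sparse cells. Report a rank test stratified by baseline intensity as a check, because it does not rely on common cut-points across baseline levels. State what is done if the model fails to converge, for example reverting to the planned model. Record the change in SAP section 4, which already lists a change to this variable.

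No new data are needed. The cost is a slightly more complex model and an odds ratio that must be described as conditional on baseline statin intensity.
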